4.7. BRIEF PAIN INVENTORY (BPI) SHORT FORM

The BPI Short Form assesses the severity of pain and its impact on functioning.

In REN001-201 the BPI questionnaire will be used at Baseline, Week 4 (Month 1), Week 12 (Month 3), Week 18 (Month 4.5) and Week 24 (Month 6). In REN001-202 subjects will be assessed at Baseline, Month 12 and Month 24; which from the start of REN001-201 are equivalent to Months 6, 18, and 30. It will also be assessed at an early termination visit if the subject withdraws from the study.

Four severity items will be investigated by the responses to the worst, least and average pain in last 24 hours and the pain right now (Questions 3, 4, 5 and 6). The higher score indicates worse pain. A pain severity score will be calculated as the mean of the non-missing 4 severity items.

In addition, the average pain interference score will be derived as the average of the responses to the 7 components to Question 9 (Cleeland 2009). If there are 3 or fewer responses, then the pain interference score will not be calculated. The higher score indicates more pain interferes with daily functioning.

For each visit changes from baseline will be calculated for the pain severity and pain interference scores.

4.8. WORK PRODUCTIVITY AND ACTIVITY IMPAIRMENT QUESTIONNAIRE: SPECIFIC HEALTH PROBLEMS (WPAI: SHP)

The WPAI questionnaire is a validated instrument to measure impairments in work and activities.

In REN001-201 the questionnaire will be used at Baseline, Week 4 (Month 1), Week 12 (Month 3), Week 18 (Month 4.5) and Week 24 (Month 6). In REN001-202 subjects will be assessed at Baseline, Months 1, 3, 6, 12, 18 and 24; which from the start of REN001-201 are equivalent to Months 6, 7, 9, 12, 18, 24 and 30. It will also be assessed at an early termination visit if the subject withdraws from the study.

Outcomes are expressed as impairment percentages, with higher numbers indicating greater impairment and less productivity, i.e., worse outcomes. There are 6 questions defined as:

Questions	Definition
1	currently employed (Yes/No)
2	hours missed because of problems associated with your PMM
3	hours missed because of other reasons
4	hours actually worked
5	how much did your PMM affect productivity while working (scale of 0 [no effect on my work] to 10 [completely prevented me from working])

Questions	Definition
6	how much did your PMM affect regular activities (scale of 0 [no effect on my daily activities] to 10 [completely prevented me from doing my daily activities])

Subjects are asked to answer Questions 2 to 6 with respect to the past 7 days.

The following 4 scores are calculated from the responses, the first 3 will only be calculated if the subject is employed:

Score	Equation
Percent work time missed due to PMM	$100 \times \frac{Q2}{(Q2 + Q4)}$
Percent impairment while working due to PMM	$100 \times \frac{Q5}{10}$
Percent overall work impairment due to PMM	$100 \times \left(\frac{Q2}{(Q2 + Q4)} + \left[\left(1 - \left(\frac{Q2}{(Q2 + Q4)} \right) \right) \times \left(\frac{Q5}{10} \right) \right] \right)$
Percent activity impairment due to PMM	$100 \times \frac{Q6}{10}$

Generally, if a response to a question used in the calculation of a score is missing, the score will be set to missing. The exception to this is the calculation of the percent overall work impairment due to PMM score; if all working hours are missed due to problems associated with PMM (i.e., Question 2≠0 and Q4=0) then $(1 - (Q2/(Q2+Q4)))=0$, and so it does not matter if Question 5 (how much did your PMM affect productivity while working) is missing or has a value. Indeed, it is anticipated that the Question 5 response will be missing if they had not worked. In such situations the percent overall work impairment due to PMM will be entirely based on work time missed due to PMM i.e., 100%.

For each visit changes from baseline for each score will be calculated.

4.9. PMM PHENOTYPIC DESCRIPTION

The phenotypic presentation of the subject's disease is rated using 3 questions taken from the Newcastle Mitochondrial Disease Adult Scale. The 3 questions relate to exercise

tolerance, gait stability and myopathy and asked in relation to the previous 4-weeks. Each question has 6 levels (0 to 5), and higher scores indicate a worse rating.

In REN001-201 the questionnaire will be used at Baseline and Week 24 (Month 6). In REN001-202 subjects will be assessed at Baseline, Months 6, 12, 18, 24, 36 and 48; which from the start of REN001-201 are equivalent to Months 12, 18, 24, 30, 42 and 54. It will also be assessed at an early termination visit if the subject withdraws from the study. Where possible the same physician should ask the questions on each occasion to ensure consistency of interpretation.

For each visit changes from baseline for each question will be calculated.

5. PHARMACOKINETIC ASSESSMENT

Plasma mavodelpar concentrations will be determined from samples taken during the study. Samples may be analysed for metabolites, but any analysis of metabolite concentrations will not be part of the CSR and are not detailed in this SAP.

At Month 1 in REN001-202 a single sample will be taken and at Months 6, 12, 18 and 24 two samples will be taken, one on arrival at site, and the second taken at the end of the visit. At Month 3 the timing of samples is dependent on the version of the protocol being used when the subject was recruited:

- Protocol Version 1: pre-dose and 1, 2, 4, 6, 8, 12 and 24 hours post-dose
- Protocol Version 2: pre-dose and 1, 2 and 4 hours post-dose

PK parameters will be calculated from the Month 3 plasma concentrations, for those subjects enrolled under Protocol Version 1.0, by an external vendor using a non-compartmental approach with WinNonlin[®] software (version 8.3 or higher). Details concerning the derivation of parameters will be documented in a separate non-compartmental analysis plan. The PK parameters estimated will include, but may not be limited to:

C_{trough}	Observed plasma concentration at 24-hours post dose (just prior to next dose)
C_{max}	Maximum observed plasma concentration over the dosing interval
T_{max}	Time of the maximum measured plasma concentration over the dosing interval. If the maximum value occurs at more than one time point, T_{max} is defined as the first time point with this value.
AUC_{τ}	The area under the plasma concentration versus time curve, over the dosing interval (i.e., 0-24 hours), as calculated using the linear trapezoidal method when concentrations are increasing and the logarithmic trapezoidal method when concentrations are decreasing

The data will also be used for a population pharmacokinetic (PK) analysis which will be detailed in a separate population PK analysis plan and reported separately.

6. SAFETY ASSESSMENTS

The primary purpose of this study is to assess the long-term safety and tolerability of dosing with mavodelpar 100 mg once daily. The sections below detail the safety assessments, including any derivations required. The analyses of the safety endpoints are detailed in [Section 10](#).

Details concerning the baseline used in the derivation of changes from baseline are provided in [Section 8.6](#).

Subjects attending sites in Germany will have additional safety assessments at Month 9 and Month 15. These safety assessments include ECGs, vital signs, safety laboratory evaluation and physical examinations. The data from these assessments will not be included in any ‘by visit’ summaries but will be listed and will be considered in summaries of results of potential clinical importance.

6.1. ADVERSE EVENTS

The incidence, causality and severity of treatment-emergent adverse events (TEAEs), including treatment-emergent serious adverse events (TESAEs) and adverse events of special interest (AESI), will be investigated.

AESI are those of scientific and medical concern specific to mavodelpar and include:

- Changes in laboratory parameters of muscle injury associated with clinically significant adverse events (AEs)
- Changes observed after baseline in formation or exacerbation of cataracts.
- Occurrence of fractures after baseline

AESI will be identified on the eCRF and will be reported in the same way as serious adverse events (SAEs).

Note in Protocol Versions 1.0 and 2.0, a spherical equivalent loss of ≥ 0.75 diopters (regardless of changes in lens clarity) was also considered an AESI and reported on the eCRF. However, since the implementation of Protocol Version 3.0 these are no longer routinely reported as AESIs.

6.2. LABORATORY EVALUATIONS

Laboratory safety samples are collected throughout the 2 studies and will be used to determine the following:

- Hematology parameters
- Biochemistry parameters, including:
 - the osteoblastic bone marker - bone specific alkaline phosphatase (BSAP)

- calcium markers - parathyroid hormone and vitamin D
- Urinalysis parameters, including:
 - the osteoclastic bone marker - Urine N-terminal telopeptide (NTx), via a morning second urinary void

Changes from baseline will be calculated for each laboratory parameter at each scheduled visit.

Laboratory values that are less than the lower limit of quantification (LLOQ) will be set to the LLOQ for the calculation of descriptive statistics. The original recorded value will be displayed in listings.

6.3. DUAL-ENERGY X-RAY ABSORPTIOMETRY (DXA) SCAN

DXA scans will be performed on a subset of subjects at Screening and Week 24 (Month 6) in REN001-201; and in REN001-202 at Baseline, Month 24 and Month 48. Therefore, subjects who have DXA scans throughout the 2 studies will have a total of 4 scans at Screening, Month 6, Month 30 and Month 54 from the start of REN001-201. For subjects who withdraw from the study, it will be performed at an early termination provided the subject has received at least 20 weeks of study drug.

To allow for scheduling of the DXA scans the REN001-201 Week 24 (Month 6) assessment can occur up to 28 days after the visit. Hence, this assessment could occur after the start of administration of mavodelpar in REN001-202; this period is not considered sufficient time to have an impact on DXA results. Therefore, for those mtDNA-PMM subjects who received placebo in REN001-201, enrolled in REN001-202 at REN001-201 Exit, enrol from study REN001-101 or for nDNA-PMM subjects this record will still be considered the baseline record relative to the start of REN001, provided it occurs within 28 days of the first dose of mavodelpar.

Baseline DXA scans will not be required for REN001-201 Exit subjects if within 6 months of the last REN001-201 scan.

The BMD, T-score and Z-score will be measured for 5 spine regions (L1-L4 and total) and for 2 hip regions (total and femoral neck).

Changes from baseline and percent changes from baseline to end of treatment will be calculated for each parameter.

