8.6 Safety Analyses

No imputation will be used for handling missing data, with the exception of conservative approaches taken for missing AE information (e.g., intensity). Details of such conventions will be documented in the SAP.

Treatment-emergent adverse events will be summarized by SOC and Preferred Term, in accordance with the MedDRA coding dictionary. The number of subjects reporting each AE preferred term will be tabulated for all TEAEs and separately for those considered as at least possibly related to study treatment by the Investigator. Number of subjects reporting SAEs and AESIs will also be tabulated.

Changes from baseline in laboratory parameters (including bone and calcium markers), vital signs, ECG and eye examinations data will be summarized by visit.

The incidence of potentially clinically significant laboratory and ECG values (e.g., increase in QTcF ≥ 30 msec from baseline or an absolute QTcF value of ≥ 500 msec).

Absolute values and changes from baseline for the DXA endpoints will be summarized. Summaries will be presented over all subjects and for the following demographic sub-groups:

- Men
- Pre-menopausal women
- Post-menopausal women

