3.2.4. Exploratory Endpoints

For mtDNA and nDNA subjects:

- Change from baseline to end of treatment in bone mineral density (BMD), as measured by Dual Energy X-ray Absorptiometry (DXA), in the following:
 - Lumbar spine (L1 to L4) BMD
 - Total hip BMD and the femoral neck BMD (in the non-dominant hip)
 - Total hip, lumbar spine, and femoral neck T-scores and Z-scores.

For nDNA-PMM subjects

- Absolute values and changes from Baseline in:
 - Distance walked during the 12-minute walk test (12MWT)*
 - MFIS Total scores and sub-scale scores*
 - Patient Global Impression of Severity (PGIS) score for fatigue and muscle symptoms
 - Brief Pain Inventory (BPI) pain severity and pain interference scores*
 - Patient-Reported Outcomes Measurement Information System (PROMIS) Short Form – Functional Assessment of Chronic Illness Therapy (FACIT) Fatigue 13a scores*
 - 36 Item Short Form Survey (SF-36) domain scores*
 - Work Productivity and Activity Impairment questionnaire: Specific Health Problem (WPAI:SHP) scores*
 - First 6-minute walk distance and last 6-minute walk distance*
 - Phenotypic description questions
- PGIC scores (muscle and fatigue symptoms)

**Collected up to Month 24 only.*

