3.5. DETERMINATION OF SAMPLE SIZE

The sample size for this study is not based on statistical justification. Recruitment of mtDNA-PMM subjects will be limited to those subjects who participated in REN001-201 or REN001-101, and reside in countries where this long-term safety study is approved. It is estimated that approximately 150 mtDNA-PMM subjects will be enrolled.

It is anticipated that up to 50 nDNA-PMM subjects may also be enrolled.

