8. GENERAL ASPECTS FOR STATISTICAL ANALYSIS

8.1. HYPOTHESIS TESTING

No formal statistical testing is planned.

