8.2. GENERAL METHODS

Continuous variables will be summarized using the number of non-missing observations (n), mean, SD, median, minimum, and maximum. Categorical variables will be summarized using counts and percentages.

Unless otherwise specified, the estimated mean and median for a set of values should be displayed to 1 more decimal place than the original values, and SD should be displayed to 2 more decimal places than the original values. The minimum and maximum should be displayed to the same number of decimal places as the original values. Deviations from this convention may arise to take account of the relevance of the precision (e.g., the distance walked in the 12MWT is reported to the nearest cm, but there is no relevance in presenting the mean to the nearest mm). These deviations from convention will be documented in the relevant analysis sections below.

Percentages will be displayed with 1 decimal place; except percentages will not be presented when the count is zero and 100% will be presented as an integer. Unless stated otherwise, percentages of subjects will be based on the number of subjects with non-missing data in the analysis set used for the presentation.

Unless stated otherwise, an on-treatment measurement will be any measurement collected (including scheduled and unscheduled visits) up to the date of last dose plus one day. Drug interruptions will not be considered, i.e., data will not be excluded during a drug interruption if the subject resumes study treatment; this includes the follow-up period for subjects who enrol in REN001-202 at the REN001-201 FU.

In by-visit summary tables, the baseline will be summarized using all available data, but also for each visit using only the baseline data from subjects with available data at the visit; hence the mean change from baseline will equal the mean observed visit value – mean baseline value.

Throughout this document ‘change from baseline’ refers to the actual change from baseline (i.e., observed visit value – baseline value). The baseline definitions are detailed in [Section 8.6](#).

There will be 3 approaches to summarising the data and, unless stated otherwise, all presentations will be presented for each approach. [Figure 1](#) in [Section 2](#) shows the different pathway options a subject can enter REN001-202 and the 5 distinct reporting groups these

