12.3. DUAL ENERGY X-RAY ABSORPTIOMETRY (DXA) SCAN

Summaries of DXA data will only be presented from the start of REN001-202 and from the start of REN001 treatment.

Observed, change from baseline and percent change from baseline values for the DXA endpoints will be summarized for the DXA set. The summary will be presented overall within the group and by sex and menopausal status (i.e., men, pre-menopausal women and post-menopausal women).

A box and whisker plot will be presented for each of the parameters measuring the total spine and the 2 hip regions (total and femoral neck), for the DXA set. The whiskers will display the 5th and 95th percentiles and outliers will be identified on the plot with subject ID. The plot will present the visits alongside one another for each group. The plot will be repeated by sex and menopausal status.

For the DXA set, the study day of the follow-up DXA scans (Months 6, 30 and 54 relative to the start of REN001-201) will be summarized using descriptive statistics.

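### The SAP applies percent change from baseline to DXA T-scores and Z-scores, for which it is not a meaningful statistic; it should be limited to BMD

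*SAP*

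**What the plan says.** SAP 6.3 lists the measurements: "The BMD, T-score and Z-score will be measured for 5 spine regions", and likewise for two hip regions. The derivation rule that follows covers all of them: "Changes from baseline and percent changes from baseline to end of treatment will be calculated for each parameter".

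SAP 12.3 carries the rule into the tables: "Observed, change from baseline and percent change from baseline values for the DXA endpoints will be summarized for the DXA set". That these endpoints include the scores is clear from SAP 3.2.4, which names "Total hip, lumbar spine, and femoral neck T-scores and Z-scores" beside the BMD measures.

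SAP 8.2 defines absolute change; the term "refers to the actual change from baseline (i.e., observed visit value – baseline value"). It gives no formula for percent change. I found no rule in the SAP for a zero or negative baseline.

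Protocol 8.6 asks for less: "Absolute values and changes from baseline for the DXA endpoints will be summarized".

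**The concern.** BMD is a positive quantity with a true zero, so percent change in BMD is a standard and interpretable summary. A DXA T-score or Z-score is the distance, in SD units, from a reference mean that is set at zero. The documents do not spell this out, but it is what the terms mean. Zero on that scale is the reference average, not an absence of bone, so a ratio to the baseline score does not measure relative change in bone.

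The practical consequence is a column that can point the wrong way, take extreme values, or be undefined for some subjects. Bone is a named question in this trial: Protocol 1.4.2.6 notes bone loss with PPAR-gamma agonists and says the effect of REN001 on BMD is unknown, and Protocol 2.4 makes bone health an exploratory objective. In the DXA tables a positive percent change means gain for BMD and may mean loss for a T-score.

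The PROMIS T-score is a separate matter. It is scaled to a mean of 50, and SAP 4.2 plans only absolute change for it.

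**Working it through.** The documents contain no figure to reproduce here. SAP 8.1 says "No formal statistical testing is planned" and SAP 3.5 says "The sample size for this study is not based on statistical justification". The check is therefore of the derivation rule itself.

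**Step 1: single subjects.** SAP 8.2 supplies the numerator. I take the usual formula, percent change = 100 × (observed − baseline) / baseline, and as a variant the same numerator over |baseline|. The scores are illustrative; the first six rows are the same loss of 0.5 units and the last is a gain of 0.5.

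| Baseline | Observed | Absolute change | Percent, usual formula | Percent, \|baseline\| |
|---|---|---|---|---|
| -2.0 | -2.5 | -0.5 | +25% | -25% |
| -1.0 | -1.5 | -0.5 | +50% | -50% |
| -0.1 | -0.6 | -0.5 | +500% | -500% |
| 0.0 | -0.5 | -0.5 | undefined | undefined |
| +0.1 | -0.4 | -0.5 | -500% | -500% |
| +1.0 | +0.5 | -0.5 | -50% | -50% |
| -1.5 | -1.0 | +0.5 | -33% | +33% |

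For example, 100 × (-1.5 − (-1.0)) / (-1.0) = 100 × (-0.5) / (-1.0) = +50%. Absolute change reads -0.5 in all six loss rows. The |baseline| variant restores the sign but leaves the ±0.1 rows at -500% and the zero row undefined.

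**Step 2: the same loss expressed in BMD.** Assume a reference mean of 1.0 and SD of 0.12 (not from the documents), so BMD = 1.0 + 0.12 × T. A 0.5-unit T-score loss is then a fall of 0.06.

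| Baseline T-score | BMD, baseline to observed | Percent change in BMD |
|---|---|---|
| -2.0 | 0.760 to 0.700 | -7.9% |
| -1.0 | 0.880 to 0.820 | -6.8% |
| -0.1 | 0.988 to 0.928 | -6.1% |
| +1.0 | 1.120 to 1.060 | -5.4% |

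The sign is right and the size stable, so percent change works for BMD and fails only for the scores.

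**Step 3: group means, illustration only.** The documents give no DXA baseline means, variances or expected set size, so every input is assumed: 40 subjects per set, true T-score loss 0.2, SD of the change 0.2, baseline SD 1.0, scores rounded to 0.1, usual formula, zero baselines dropped.

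| Assumed baseline mean | Negative baselines | Average of the mean percent change | Sets with a positive mean |
|---|---|---|---|
| -1.0 | 83% | about +14% | about 88% |
| -0.5 | 67% | about +9% | about 74% |
| 0 | 48% | about 0% (90% range about -27% to +27%) | about 50% |

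Between 2% and 4% of subjects have a baseline of exactly 0.0. Mean absolute change was negative in every simulated set. Medians, which SAP 8.2 also requires, do not rescue the column: at a baseline mean of -1.0 the median percent change was positive in about 99% of sets.

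The result is sensitive to the inputs. If the SD of 0.2 applies to each scan instead of to the change, the share of sets with a positive mean falls to about 80%, 63% and 42% for the three baseline means.

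**The case against.** The best case for leaving the plan alone is that little depends on this column.

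- **Correct figures stand beside it.** SAP 12.3 puts observed values, absolute change and percent change in one summary, and SAP 8.2 puts changes from baseline in the listings. Absolute T- and Z-score change and BMD percent change keep the right sign, so a careful reader would see the contradiction. This stands.
- **The endpoint carries little weight.** DXA is optional (Protocol 4.4), exploratory (SAP 3.2.4) and untested (SAP 8.1), with no decision rule attached. This stands.
- **The SAP does not write the formula that reverses the sign.** This stands in part. The reversal follows from the usual signed denominator, not from a formula in the SAP. No other convention is stated, however, and |baseline| would leave the instability near zero and the undefined case.
- **Adding percent change to the protocol's list is allowed.** Protocol 8 permits further analyses in the SAP, so the difference from Protocol 8.6 is not itself a fault. This stands.

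A reader might also infer that subjects with low bone mass are the worst distorted, or that post-menopausal women are the most exposed. The documents do not support either. The sign flips at -0.1 as surely as at -2.5, and the distortion in size is greatest near zero: a loss of 0.2 gives 100 × (-0.2)/(-0.1) = +200% from -0.1, but 100 × (-0.2)/(-2.5) = +8% from -2.5. No baseline DXA values are given for any subgroup. Protocol 1.4.2.6 and 4.2 also describe exclusions for fragility or stress fracture and for osteoporosis not adequately addressed, so how negative the baseline scores will be is unknown.

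Reading the rule in SAP 6.3 as covering BMD only is not tenable, because the list immediately before it names all three measures.

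**Conclusion.** The point holds as a minor correction. As written, the SAP derives and tabulates percent change for T-scores and Z-scores, and the statistic is unsuitable for a scale centred on zero whichever denominator is used. With the usual formula it reverses sign for every negative baseline. With either formula it is unstable near zero and undefined at zero.

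It would be going too far to say that the bone-health assessment is compromised, or that the trial will report bone loss as gain. The valid measures are in the same summary, and the conclusion on bone need not use the faulty column. The single-subject results rest only on the formula and on the standard meaning of the scores. The group-level percentages rest wholly on assumed inputs and are not an estimate for this trial.

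**What to change.** In SAP 6.3, limit percent change from baseline to BMD (lumbar spine, total hip, femoral neck) and derive only absolute change for T-scores and Z-scores. In SAP 12.3, make the same restriction in the summary: observed, absolute and percent change for BMD; observed and absolute change for T-scores and Z-scores.

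The cost is one sentence in each section and a matching edit to the table shells. It needs no new data and leaves fewer output columns.
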